8.5 HRUA-HAE Analyses

Objective 1

- Table H.1:
 Number of Hospitalizations by Treatment Sequence, Period and Study Visit
- Table H.2:Number of Provider Visits by Treatment Sequence, Period, and Visit
- Table H.3: Number of Tests Required by Treatment Sequence, Period, and Study Visit
- Table H.4: Number of ER/Urgent Care Visits by Treatment Sequence, Period and Study Visit
- Table H.5: Number of Days of Home Care by Treatment Sequence, Period, and Study Visit

9. LIST OF FIGURES

9.1 Objective 1

- Figure 1.1.1: Line Plot of Mean Angioedema Quality of Life Questionnaire Total Scores With Standard Error, by Treatment Sequence, Period, and Study Visit
- Figure 1.1.2: Line Plot of Mean Angioedema Quality of Life Questionnaire Functioning Scores With Standard Error, by Treatment Sequence, Period, and Study Visit
- Figure 1.1.3: Line Plot of Mean Angioedema Quality of Life Questionnaire Fatigue-Mood Scores With Standard Error, by Treatment Sequence, Period, and Study Visit
- Figure 1.1.4: Line Plot of Mean Angioedema Quality of Life Questionnaire Fear-Shame Scores With Standard Error, by Treatment Sequence, Period, and Study Visit
- Figure 1.1.5: Line Plot of Mean Angioedema Quality of Life Questionnaire Nutrition Scores With Standard Error, by Treatment Sequence, Period, and Study Visit
- Figure 1.2.1: Line Plot of Mean Work Productivity and Activity Impairment General Health Questionnaire Absenteeism Domain Scores With Standard Error, by Treatment Sequence, Period, and Study Visit
- Figure 1.2.2: Line Plot of Mean Work Productivity and Activity Impairment General Health Questionnaire Presenteeism Domain Scores With Standard Error, by Treatment Sequence, Period, and Study Visit
- Figure 1.2.3: Line Plot of Mean Work Productivity and Activity Impairment General Health Questionnaire Work Productivity Loss Domain Scores With Standard Error, by Treatment Sequence, Period, and Study Visit
- Figure 1.2.4: Line Plot of Mean Work Productivity and Activity Impairment General Health Questionnaire Activity Impairment Domain Scores With Standard Error, by Treatment Sequence, Period, and Study Visit
- Figure 1.3.1: Line Plot of Mean Sheehan Disability Scale Total Scores with Standard Error, by Treatment Sequence, Period and Study Visit
- Figure 1.3.2: Line Plot of Mean Sheehan Disability Scale Work/School Domain Scores with Standard Error, by Treatment Sequence, Period and Study Visit Line
- Figure 1.3.3: Line Plot of Mean Sheehan Disability Scale Social Life/Leisure Activities Domain Scores with Standard Error, by Treatment Sequence, Period and Study Visit
- Figure 1.3.4: Line Plot of Mean Sheehan Disability Scale Family Life/Home Responsibilities Domain Scores with Standard Error, by Treatment Sequence, Period and Study Visit

Figure 1.4.1: Line Plots of Mean Weekly Average Angioedema Activity Daily Scores with Standard Error, by Treatment Sequence, Period, and Study Visit

9.2 **Objective 3**

- Figure 3.1.1: Proportion of Subjects Reaching an Improvement Greater Than or Equal to the Responder Definition of One-half a Standard Deviation of the Common Baseline for Change in Angioedema Quality of Life Questionnaire Scores from Baseline to Week 13 by Treatment Sequence and Period
- Figure 3.1.2: Proportion of Subjects Reaching an Improvement Greater Than or Equal to the Responder Definition of 6 for Change in Angioedema Quality of Life Questionnaire Scores from Baseline to Week 13 by Treatment Sequence and Period
- Figure 3.2: Proportion of Subjects Reaching an Improvement Greater Than or Equal to the Responder Definition for Change in Weekly Average Angioedema Activity Score from Baseline (Day 1) to Week 14 by Treatment Sequence and Period

10. PROGRAMMING CONVENTIONS

10.1 Study Measure Scoring

10.1.1 Angioedema Quality of Life (AE-QoL) Questionnaire

The questionnaire will be scored according to the developers' guidelines (Weller et al., 2012) to produce a total score and four domain scores (functioning, fatigue/mood, fear/shame, nutrition). Raw domain scores (mean of the item scores within each scale) and the raw total score (mean of all item scores) will be rescaled using linear transformations into final percentage scores ranging 0 to 100, based on the maximum possible score, where the higher the score the greater the QoL impairment.

Final variables for analysis (per time-point and per study period):

- 1. Rescaled AE-QoL total score
- 2. Rescaled AE-QoL functioning domain score
- 3. Rescaled AE-QoL fatigue/mood domain score
- 4. Rescaled AE-QoL fear/shame domain score
- 5. Rescaled AE-QoL nutrition domain score

10.1.2 EuroQol 5-dimensional 5-level (EQ-5D-5L) Descriptive System and EQ Visual Analogue Scale (EQ-VAS)

The EQ-5D-5L index score will be calculated using the developers' algorithm based on countryspecific reference score sets developed (Van Hout et al., 2012). Score sets are available for Denmark, France, Germany, Japan, Netherlands, Spain, UK, US and Zimbabwe. For countries in which no score set exists (Canada, Hungary, Israel, Romania, and Sweden) the closest neighboring country will be used as a proxy (EuroQol Group, 2015).

The EQ-VAS is a measure of overall self-rated health status, used and analyzed separately from the index score. The EQ-VAS ranges from 0 to 100, with higher scores indicative of better overall health.

Final variables for analysis (per time-point and per study period):

- 1. EQ-5D-5L index score
- 2. EQ-VAS score

10.1.3 Work Productivity and Activity Impairment – General Health (WPAI-GH)

The WPAI-GH will be scored for each assessment according to the scoring guidelines listed below (Reilly et al., 1993):

- 1. Absenteeism (work time missed = (Q2/(Q2+Q4))*100)
- 2. Presenteeism (impairment at work or reduced on-the-job effectiveness = (Q5/10)*100)
- 3. Work productivity loss (overall work impairment/absenteeism plus presenteeism = (Q2/(Q2+Q4)+[(1-(Q2/(Q2+Q4)))x(Q5/10)])*100)
- 4. Activity Impairment = ((Q6/10)*100)

Final variables for analysis (per time-point and per study period):

- 1. Absenteeism score
- 2. Presenteeism score
- 3. Work productivity loss score
- 4. Activity impairment score

10.1.4 Sheehan Disability Scale (SDS)

The raw scores for impairment in work/school, social life/leisure activities, and family life/home responsibilities will be rescaled to a percentage of the maximum possible score (maximum score is 10). A total global functioning impairme7nt score is calculated as the sum of the three raw work/school, social life/leisure activities, and family life/home responsibilities scores. This is also rescaled to a percentage of the maximum possible score (maximum score is 30) (Sheehan, 1983).

Final variables for analysis (per time-point and per study period):

- 1. Rescaled SDS total global functioning score
- 2. Rescaled SDS work/school score
- 3. Rescaled SDS social life/leisure activities score
- 4. Rescaled SDS family life/home responsibilities score

10.1.5 Angioedema Activity Score (AAS)

The final AAS daily score is the sum of the five items (Weller et al., 2013). This is calculated for each day the instrument is administered.

The following summary scores will be calculated:

- 1. The total disease activity score for the full duration of a study period = the sum of each final daily score post-baseline in each 14-week study period.
- 2. The overall average for the full duration of a study period = the mean of all the final daily scores post-baseline in each 14-week study period.
- 3. The weekly average daily disease activity scores = the mean of all the final daily scores post-baseline in each week individually.

Final variables for analysis:

- 1. Daily final AAS score (per day and per study period)
- 2. Weekly daily average final AAS score (per week and per study period)
- 3. Overall total AAS score (per study period)
- 4. Overall average AAS score (per study period)

10.1.6 Healthcare Resource Utilization Assessment related to HAE (HRUA-HAE)

The raw values are used. The total values for the entire treatment period are calculated by summing the responses to all assessments during that period for each item separately.

Final variables for analysis (per time-point and total, and per study period):

- 1. Number of hospital admissions
- 2. Number of healthcare provider visits
- 3. Number of tests required
- 4. Number of emergency medicine unit or out-of-hours care clinic visits
- 5. Number of days of home care

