7.1.2.1 Visit 1a (predose)

The following procedures will be performed at the investigative site prior to the first dose of investigational product at Visit 1a:

- Collection of AEs
- Randomization
- Physical examination
- Vital signs (≤ 30 min before the start of injection)
- Clinical laboratory testing (biochemistry, hematology, coagulation)
- Urinalysis testing with microscopy
- Urine pregnancy test (in females of childbearing potential)
- Recording of concomitant medications (needed for confirmation of subject eligibility)
- PK (C1 INH antigen, C1 INH functional, [includes measurement of C1q]) and PD (C4) sampling (within ≈ 15 min)
- Immunogenicity (anti-C1 INH antibody)
- Angioedema quality of life (AE-QoL) questionnaire, EuroQol 5-dimensional 5-level

descriptive system (EQ-5D-5L), Work Productivity and Activity Impairment-General Health (WPAI-GH) questionnaire, and Sheehan Disability Scare (SDS) assessments recorded in the electronic subject diary

- Health resource utilization assessment (HRUA)-HAE

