7.1.3.1 Visit 1b (predose)

The following procedures will be performed at the investigative site prior to the first dose of investigational product in Treatment Period 2 at Visit 1b:

- Collection of AEs
- Physical examination
- Vital signs (\leq 30 min before the start of injection)
- Clinical laboratory testing (biochemistry, hematology, coagulation)
- Urinalysis testing with microscopy
- Urine pregnancy test (in females of childbearing potential)
- Recording of concomitant medications
- PK (C1 INH antigen, C1 INH functional) and PD (C4) sampling (within \approx 15 min)
- Immunogenicity (anti-C1 INH antibody) blood sample collection
- AE-QoL, EQ-5D-5L, WPAI-GH, and SDS assessments recorded in the electronic subject diary
- HRUA-HAE

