12.3 Health-related Quality of Life Analyses

Details of the health-related quality of life analyses will be documented in a quality of life SAP. The health-related quality of life analyses will be summarized using the Full Analysis Set.

The AE-QoL is a questionnaire on the quality of life of patients suffering from recurrent angioedema. It consists of 17 specific questions that are associated with work, physical activity, free time, social relations, and food. Subjects will be asked how often they were restricted by— as well as the difficulties and problems that could be associated with—recurrent swellings (angioedema) during the previous 4 weeks. The result of the AE-QoL questionnaire is specified as a secondary efficacy endpoint (see Section 10.3).

The EuroQol 5-dimensional 5-level descriptive system (EQ-5D-5L) is a descriptive system of health-related quality of life states consisting of 5 dimensions (mobility, self-care, usual activities, pain/discomfort, anxiety/depression), each of which can take 1 of 5 responses. The responses record 5 levels of severity within a particular dimension. Results of the EQ-5D-5L health status instrument will be summarized on each question using descriptive statistics in accordance with the EQ-5D-5L user guide (version 2.0) by treatment and visit.

The Work Productivity and Activity Impairment-General Health (WPAI-GH) questionnaire includes 6 questions about work and activity impairment due to health problems during the past 7 days. Outcomes are expressed as impairment percentages, with higher numbers indicating greater impairment and less work or productivity. Results of the WPAI-GH questionnaire will be summarized on each question using descriptive statistics by treatment and visit.

CONFIDENTIAL

Shire SHP616-300 Statistical Analysis Plan idursulfase IT

Study personnel will ask subjects specific questions regarding their utilization of health care resources for the management of their HAE disease. Assessment (HRUA-HAE) will be completed at the time points specified protocol. Study personnel will enter the survey response into the eCRF. Results of the HRUA-HAE will be summarized on each question using descriptive statistics by treatment and visit.

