4.2.6 Healthcare Resource Utilization Assessment related to HAE (HRUA-HAE)

The usage of healthcare resources related to HAE in the last month (HRUA-HAE) is assessed (every four weeks) with a 5-item questionnaire collecting:

- i. Number of hospital admissions
- ii. Number of healthcare provider visits
- iii. Number of tests required
- iv. Number of emergency medicine unit or out-of-hours care clinic visits
- v. Number of days of home care

The total number of hospital admissions, healthcare provider visits, tests required, emergency/out-of-hours clinic visits, and days of home care will be calculated, using the information collected in the HRUA-HAE, for the duration of each study period by summing all of the responses to each individual item during each period.

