4.3 Study Assessments

The administration of study measures for each study period will follow the schedule of assessments provided in the study protocol (see Table 1 and Table 2). The PRO measures will be completed using the electronic subject diary and will be assessed as follows:

AE-QoL: Administered every 4 weeks on weeks 1 (prior to treatment administration), 5, 9, and 13, of each study period. It will also be administered at the early discontinuation visit, if applicable, and at the 1-week post-treatment visit.

EQ-5D-5L: Administered on weeks 1 (prior to treatment administration), and 12, of each study period, and on each day subjects experience signs or symptoms of AE attack. It will also be administered at the early discontinuation visit, if applicable, and at the 1-week post-treatment visit.

WPAI-GH: Administered on week 1 (prior to treatment administration) and once a week, for the duration of each study period. It will also be administered at the early discontinuation visit, if applicable, and at the 1-week post-treatment visit.

SDS: Administered on week 1 (prior to treatment administration) and once a week, for the duration of each study period. It will also be administered at the early discontinuation visit, if applicable, and at the 1-week post-treatment visit.

AAS: Administered daily. It will also be administered at the early discontinuation visit, if applicable, and at the 1-week post-treatment visit.

HRUA-HAE: Administered on weeks 1 (prior to treatment administration), 4, 8, and 12, of each study period. It will also be administered at the 1-month post-treatment visit.

Shire HRQoL Statistical Analysis Plan Protocol SHP616-300

22 Aug 2017

Table 1: Schedule of Assessments – Study period 1

													STUD	OY PE	RIOD) 1 (B)	Y STU	DY W	EEK))									
			1		2		3		4		5		6		7		8	ç)	1	.0	1	1		12	1	3	14	4
														DOS	ING V	/ISIT:	S (1a to	o 28a)											
Procedures	Screen ^a	1a	2a	3a	4 a	5a	6a	7a	8 a	9a	10a	11a	12a	13a	14a	15a	16a	17a	18a	19a	20a	21a	22a	23a	24a	25a	26a	27a	28a
Informed consent	~																												
Medical history	~																												
Inclusion/Exclusion criteria	~	✔ c																											
Adverse events ^b	~		¥																									~	
Randomization (predose)		✓ c																											
Physical examination	~	✓ c							~								<								•				~
Prior/concomitant meds	~	✓ c	~	~	~	~	~	~	~	~	~	~	~	<	~	~	<	~	~	~	~	<	~	<	<	~	<	~	~
Height and body weight	~																												

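### HRUA-HAE period totals count the predose Visit 1a and 1b answers, so in A/B and B/A the Period 2 total includes about a month of use on the other treatment

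*SAP*

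**What the plan says.** HRQoL SAP 4.2.6 gives the recall window and the frequency: "The usage of healthcare resources related to HAE in the last month (HRUA-HAE) is assessed (every four weeks". The same section says that period totals are calculated "for the duration of each study period by summing all of the responses to each individual item during each period", and HRQoL SAP 10.1.6 repeats the rule: "The total values for the entire treatment period are calculated by summing the responses to all assessments during that period for each item separately". It lists the total, alongside the value at each time point, as a final variable for analysis.

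HRQoL SAP 4.3 says which assessments belong to a period: "HRUA-HAE: Administered on weeks 1 (prior to treatment administration), 4, 8, and 12, of each study period". The protocol agrees. Sections 7.1.2.1 and 7.1.3.1 list HRUA-HAE among the procedures done "prior to the first dose of investigational product at Visit 1a" and "prior to the first dose of investigational product in Treatment Period 2 at Visit 1b" respectively. Protocol 3.1 sets two 14-week periods with no washout between them.

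Two neighbouring rules bear on this. HRQoL SAP 5.1.2 treats Visit 1b as the Period 2 baseline for analyses other than the mixed models. HRQoL SAP 10.1.5, just before the HRUA-HAE rule, limits the AAS period total to post-baseline scores. Section 10.1.6 has no such limit.

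The planned output is descriptive. HRQoL SAP 3.2 sets the objective of describing absolute values by treatment, period and sequence. Tables H.1 to H.5 are laid out by sequence, period and visit. Main SAP 12.3 adds: "Results of the HRUA-HAE will be summarized on each question using descriptive statistics by treatment and visit".

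**The concern.** A period total should measure resource use during that period. One of its four components cannot, because it is collected before the period's first dose and looks back a month. In Period 1 that component is pre-study use. In Period 2 it is roughly the last month of Period 1. For A/B subjects, active-time use therefore enters the placebo total, and for B/A subjects placebo-time use enters the active total.

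At stake is the description of hospital admissions, provider visits, tests, emergency or out-of-hours visits and home-care days by treatment. Anyone who compares the totals between treatments, or reuses them in a cost analysis, would be comparing partly mixed exposures without being told so.

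**Working it through.** The documents state no figure for these totals, so there is none to reproduce. The check has two parts.

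**1. What each answer covers**

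Inputs: twice-weekly dosing (Protocol 6.2), taken as one dose every 3.5 days; 14-week periods (Protocol 3.1); last-month recall (HRQoL SAP 4.2.6), taken as 28 to 30.4 days. Visit k falls on period day 1 + 3.5(k-1).

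- Visit 8: day 25.5. Visit 16: day 53.5. Visit 24: day 81.5.
- Visit 1b: Period 1 day 98 + 1 = 99. Its recall starts at 99 - 28 = 71 or 99 - 30.4 = 68.6, so it covers about days 69 to 99 of Period 1 and none of Period 2.
- Overlap of Visit 1b recall with the time up to Visit 24a: 81.5 - 71 = 10.5 days, or 81.5 - 68.6 = 12.9 days.
- Visit 8b comes 24.5 days after Visit 1b, so its recall reaches 28 - 24.5 = 3.5 or 30.4 - 24.5 = 5.9 days back into Period 1.

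**2. Expected totals**

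Let a, b and h be monthly use on active, on placebo and before the study. Assume constant rates, no period effect and one month of use per answer.

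| Sequence | Period 1 total | Period 2 total |
|---|---|---|
| A/B | h + 3a | a + 3b |
| B/A | h + 3b | b + 3a |
| A/A | h + 3a | 4a |

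With the predose answers left out, each total is 3a or 3b and the placebo-minus-active difference is 3(b-a) everywhere. As written it is:

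- Within A/B: (a + 3b) - (h + 3a) = 3(b-a) + (a-h).
- Within B/A: (h + 3b) - (b + 3a) = 3(b-a) + (h-b).
- Averaged over A/B and B/A: 3(b-a) - (b-a)/2 = 2.5(b-a). The h terms cancel. Loss 0.5/3 = 16.7%.
- Within Period 2: (a + 3b) - (b + 3a) = 2(b-a). Loss 1/3 = 33.3%.
- Within Period 1: (h + 3b) - (h + 3a) = 3(b-a). No loss.
- With A/A pooled at 26/26/14 (HRQoL SAP Exhibit A), the active mean is [26(h + 3a) + 26(b + 3a) + 14(h + 3a) + 14(4a)]/80 = 0.5h + 0.325b + 3.175a. The placebo mean is [26(a + 3b) + 26(h + 3b)]/52 = 0.5h + 0.5a + 3b. The difference is 2.675(b-a). Loss 0.325/3 = 10.8%.

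**Illustration with a = 1 and b = 2 (assumed).** The A/B-B/A difference is 2.5 instead of 3. The active-to-placebo ratio of mean totals is 4.5/7 = 0.64 if h = 1, or 5/7.5 = 0.67 if h = 2, instead of 0.50.

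**The case against.** The strongest reply is that little depends on the total. HRUA-HAE has one descriptive objective, and HRQoL SAP 6.4.2 allows only informal assessment of a treatment effect. Tables H.1 to H.5 report by visit, and none is titled as a period total. This stands as a limit on the consequence: the shrinkage applies to a difference that the plan does not commit to computing. It does not remove the defect, because the total is a listed final variable and its rule is wrong for its purpose.

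A second reply is that Visit 1b is already named the Period 2 baseline, so a programmer would leave it out. The text does not say so. Section 4.3 counts the predose assessment among those of each period, and the AAS rule shows that the authors wrote in a post-baseline limit where they wanted one.

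A reader might go further and infer any of the following. The documents do not support them.

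- *Every total mixes in another treatment or pre-study care.* In A/A Period 2 the Visit 1b answer covers the same treatment.
- *The treatment contrast is always pulled toward zero.* Within Period 1 it is unbiased. Within a single sequence the direction depends on the pre-study rate.
- *Main SAP 12.3 makes the same error.* It tabulates by visit, so nothing is summed. The Visit 1b row would sit under the Period 2 treatment while describing Period 1, which is a labelling problem.
- *Visit 1b simply belongs in the Period 1 total.* That would count 10.5 to 12.9 days twice. It would also be asymmetric, because the next assessment after Visit 24b is a month after the last dose.

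**Conclusion.** The summing rule is wrong as written and should be corrected, with modest consequences. It places about a month of other-treatment use in the Period 2 totals of A/B and B/A, and about a month of pre-study use in every Period 1 total. Under the stated assumptions, the difference in totals falls by 17% averaged over the two crossover sequences, 33% within Period 2 and 11% with A/A pooled.

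These percentages illustrate the rule and do not predict the trial's data. They need constant rates, no period effect and one month of use per answer. The recall window rests on HRQoL SAP 4.2.6 alone: the questionnaire is not in the documents, and Protocol 7.2.4.3 gives no recall period. No primary, key secondary or other tested endpoint is affected.

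**What to change.** - In HRQoL SAP 4.2.6 and 10.1.6, limit the period total to the post-baseline assessments (Visits 8, 16 and 24). Express it per completed assessment, so that subjects who leave early or miss a visit are comparable. State that it covers about 12 of the 14 weeks.
- In Tables H.1 to H.5 and in the main SAP 12.3 summary, show Visits 1a and 1b separately, labelled as use before that period's first dose.
- Do not add Visit 1b to the Period 1 total.

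The cost is SAP wording and minor programming, with no new data. Two small downsides should be stated: roughly the last two weeks of each period are outside the total, and Visit 8b recall still reaches about 3.5 to 6 days into Period 1.

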19.2 Derivation of normalized efficacy endpoints

Any subject who completes a treatment period should provide data with which to derive efficacy scores. Thus, for each individual treatment period, the normalized efficacy scores are calculated as below:

 X_i = Number of **days** of participation in that treatment period for Subject *i*,

 $Y_i = \mathbf{RAW}$ Efficacy Score expressing the cumulative period score for Subject *i*,

 Y^*_i = **NORMALIZED** Efficacy Score for Subject *i*, (the normalized score expressed as score

per **Month**), which is calculated as $(Y_i / X_i) * 30.4$

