10.2 Calculating Change in Scores

Change in scores will be calculated as follows for each visit and each study period separately:

- Study period 1:
 - Follow up visit x score baseline (visit 1a) score
- Study period 2:
 - Follow up visit x score baseline (visit 1b) score

Change in AAS scores will be calculated as follows:

- Study period 1:
 - Weekly average daily scores for the each week of follow up baseline (visit 1a) daily score
- Study period 2:
 - Weekly average daily scores for the each week of follow up baseline (visit 1b) daily score

The overall change score is always the final follow up visit minus the baseline visit, for each study period separately. For AAS scores, it is change from baseline to the weekly average daily score in the final week, for each study period separately.

Imputation of missing data will be limited to end of treatment data used in the calculation of change scores. In the event that a subject is missing end of treatment data, the closest available score to the period end or discontinuation will be used so long as the value was obtained a minimum of 9 weeks past the period start date. If not available, no change score will be calculated. No other missing data will be imputed.

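### HRUA-HAE period totals are plain sums with no adjustment for months observed and no rule for partial periods, so totals for subjects who stop early are biased downward

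*SAP*

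**What the plan says.** HRQoL SAP section 10.1.6 builds the period total for each of the five HRUA-HAE items this way: "The total values for the entire treatment period are calculated by summing the responses to all assessments during that period for each item separately". Section 4.2.6 says the same, describing totals "for the duration of each study period by summing all of the responses to each individual item during each period". Section 10.1.6 lists these totals, beside the per-visit values, as final analysis variables.

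Each response recalls the last month (HRQoL SAP section 4.2.6). The schedule in section 4.3 reads: "HRUA-HAE: Administered on weeks 1 (prior to treatment administration), 4, 8, and 12, of each study period". On the only other occasion, section 4.3 says: "It will also be administered at the 1-month post-treatment visit". The early discontinuation visit is not mentioned there for this measure, Protocol Table 3 leaves it unticked, and Protocol section 7.1.4 omits it.

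HRQoL SAP section 5.1.3 has missing-data rules for the AE-QoL, EQ-5D-5L, EQ-VAS, WPAI-GH, SDS and AAS, but none for the HRUA-HAE. Imputation is limited to end-of-treatment values used in change scores, after which section 10.2 says: "No other missing data will be imputed".

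**The concern.** A total labelled as covering a whole treatment period should mean the same thing for every subject. Here it depends on how many monthly responses were obtained. A subject who stops between weeks 4 and 8 has one on-treatment response and a completer has three. Use between the last scheduled assessment and stopping is not captured as on-treatment use, because the post-treatment response recalls a month after dosing has ended.

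Stopping may also be related to the outcome. Protocol section 4.4.1 lists lack of efficacy as a reason. Protocol section 5.2.1 describes discontinuation, after at least 3 weeks of product, in adults previously on C1 INH prophylaxis whose attacks and quality of life worsen. If such stops are more frequent on placebo, the placebo totals are pulled down further than the active totals.

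The plan handles other cumulative measures differently. The NNA is divided by days on treatment (main SAP section 10.1). Main SAP section 19.2 normalizes severity, attack-free days, treated attacks and the AAS by "Number of days of participation in that treatment period for Subject". In the HRQoL SAP, the AAS period total has a period average beside it (section 10.1.5). The HRUA-HAE total has no such counterpart.

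**Working it through.** The documents give no numerical figure for HRUA-HAE totals, so there is none to reproduce.

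**Inputs.** On-treatment assessments per period: 3 (weeks 4, 8 and 12), plus a predose response at week 1 (HRQoL SAP section 4.3). Crossover subjects: 26 + 26 = 52 randomized (main SAP Table 1) and 44 planned completers (main SAP section 2.5), so 8 of 52 = 15.4% planned non-completion. The use rates below are assumptions.

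**One subject.** With a constant monthly rate and *k* on-treatment assessments completed, the raw total as a share of a completer's is *k*/3, or (*k*+1)/4 if the predose response is also summed.

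| *k* | on-treatment only | with predose response |
|---|---|---|
| 0 | 0% | 25% |
| 1 | 33% | 50% |
| 2 | 67% | 75% |

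Dividing by assessments completed restores the true monthly rate for *k* = 1 or 2. For *k* = 0 no on-treatment rate exists.

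**When a stopper still scores higher than a completer.** With relative use *r* and on-treatment responses only, *k* × *r* > 3 requires *r* > 3 for *k* = 1, or *r* > 1.5 for *k* = 2. It is impossible for *k* = 0.

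**Group mean.** Assume 8 of 52 subjects stop in the same period and completers use 1 unit per month. The full mean is (44×3 + 8×3×*r*)/52 and the raw mean is (44×3 + 8×*k*×*r*)/52.
- *r* = 1: shortfall 24/156 = 15.4%, 16/156 = 10.3% and 8/156 = 5.1% for *k* = 0, 1 and 2.
- *r* = 3: shortfall 72/204 = 35.3%, 48/204 = 23.5% and 24/204 = 11.8%.

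**Treatment difference, as an illustration.** Assume that all losses fall in placebo periods, each captures 1 of 3 assessments, and the active mean is half the placebo completer mean. With loss fraction *d*, the true difference is (1−*d*) + *d r* − 0.5 and the raw difference is (1−*d*) + *d r*/3 − 0.5.

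| *d* | *r* | true | raw | understated by |
|---|---|---|---|---|
| 4/52 | 1 | 0.500 | 0.449 | 10.3% |
| 4/52 | 2 | 0.577 | 0.474 | 17.8% |
| 8/52 | 1 | 0.500 | 0.397 | 20.5% |
| 8/52 | 2 | 0.654 | 0.449 | 31.4% |

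**The case against.** The strongest reply is that no planned output uses the total. The HRUA-HAE objective (HRQoL SAP section 3.2) is descriptive, section 6.4.2 summarizes values at each assessment, and Tables H.1 to H.5 are by visit. Each by-visit value is already one month's use, a missing visit lowers n and adds no zero, and the table shell has an n row. Main SAP section 12.3 is also by treatment and visit. This stands, and it limits the reach of the point. It does not remove it, because section 10.1.6 names the totals as final analysis variables and states a derivation for them.

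A reader might go further than the documents allow in three ways.

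- **That missing months are imputed as zero use.** The SAP does not say so. Summing what was collected has that arithmetic effect, but a programmer could equally set a partial total to missing. The text does not settle which.
- **That early stoppers will look like the lightest users.** The bias is downward, but a stopper with more than 3 times the completer rate (1 of 3 assessments) or more than 1.5 times (2 of 3) still has the higher total. Only stops before week 4 give an on-treatment total of zero whatever the rate.
- **That a treatment contrast could reverse.** No contrast on totals is planned. Even the most extreme case above keeps 69% of the difference, with its sign unchanged.

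Two further points are fair. The deterioration route in Protocol section 5.2.1 covers only adults previously on C1 INH prophylaxis and follows discussion with the sponsor. And the 8 of 52 is an allowance across both periods and both treatments, so placing all of it in placebo periods is a worst case.

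**Conclusion.** The point holds as a minor defect in a stated derivation. As written, the HRUA-HAE total is biased downward for any partly observed period and is not comparable with a completer's total. At a constant monthly rate it is 33% or 67% of the completer value with 1 or 2 of 3 on-treatment assessments, or 50% or 75% with the predose response included; the wording does not settle whether that response belongs.

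The direction between treatments depends on where stopping occurs. More stopping on placebo would understate placebo use, which works against the active product. The 10% to 31% range for a treatment difference is illustrative only: it rests on all losses falling in placebo periods, active treatment halving use, and one assessment captured per loss. The by-visit tables and all tested endpoints are unaffected.

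**What to change.** In HRQoL SAP sections 4.2.6 and 10.1.6, replace the period total, or accompany it, with use per month observed. For each item, divide the sum of on-treatment responses by the number of on-treatment assessments completed, or by days covered/30.4. Naming on-treatment responses also keeps the predose week-1 response, which recalls the month before the period, out of the figure. Show the number of contributing assessments by treatment, and set a period with no on-treatment assessment to missing.

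The cost is a few lines of wording and a simple derivation, with no new data collection. Rates based on one assessment are noisier, which the displayed counts will make visible. The change removes the effect of period length; it cannot recover use in months that were never observed.
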